#### **d. Intended Demographics**

We propose to recruit 1800 inpatient or outpatient youth (ages 8-19 years, inclusive) who have a BMI  $\geq 85\text{-ile}$  (i.e., overweight or obese) and are prescribed SGAs as either ongoing or new treatment. There will be no barriers to inclusion based on sex, race, ethnicity or clinical status with the exception that otherwise eligible patients with current or prior therapeutic MET exposure will be excluded. We anticipate equal recruitment by sex, and based on US census reports from the recruitment regions, approximately 25% non-White (20% African American/Black and 5% Asian) and 15% Hispanic youth. Because the diagnosis of BSD and the use of SGAs is more controversial in younger patients and there are little safety data regarding the use of MET in patients younger than 8 years old, we restrict our sample to 8-19 year olds.

Process for consenting Spanish speaking caregivers: If it is determined that a caregiver cannot be properly consented in English, the caregiver will receive a consent document translated into Spanish. A qualified translator will be present to answer any questions the caregiver may have about the study. A qualified translator can be a bilingual study staff member, or a certified translator. A progress note will be written indicating a qualified translator was present at time of consent. The progress note will remain attached to the signed consent form.

#### **e. Study Population Source**

Participants will be recruited from approximately 40 community-based mental health treatment centers, some of which have multiple locations.

#### **f. Recruitment Plans**

Because our study is a large pragmatic patient-centered trial, we have minimal eligibility requirements, which should facilitate the feasibility of recruitment. Each selected clinical site is a large mental health practice that has more than 100 youth eligible for study participation. Therefore, we should have no difficulty reaching our proposed rate of recruitment of 1-2 patients/month/site at 40 sites and over the course of 57 months. In general, study visits will coincide with clinical visits, so we anticipate that retention will be at least as good as in our prior naturalistic outcome studies (~90%) over 2 years. Each week study sites will send their screening logs to the lead site that identify potential patients and will collect ethnicity information.

We will create a study website that will have the address of [www.mobilitystudy.org](http://www.mobilitystudy.org). This website will be used as a communication tool to post important study related material and information to committee/stakeholder members, study sites, and patients enrolled in the study. A Login username and password will be required to view study specific material related to interventions, meeting material, and videos. There will be information about the study that will be available for the public to view, including information about the study, metformin, and bipolar spectrum disorders.

We will have a study Twitter account for the MOBILITY study that will be used to disseminate information about the study. This will not be used as a means of recruitment. We will use the handle name @MOBILITY\_Trial, to communicate information about the study to likely followers, including clinicians, researchers, members of the media and study participants and their families. The account will not provide medical or health advice or recommendations. It will provide background information about the study; background information about Metformin; and information about any publications or webinars related to the study. It could provide links to other research that is published during the next 5 years related to Metformin, SGAs and bipolar disorder in adolescents. We anticipate posting one tweet per week. Tweets will be reviewed prior to publication by [name], or a study-related personnel designated by her.

## **G. RISK TO SUBJECTS**

### **a. Level of Risk Description**

Potential risks from study participation include possible risks from MET treatments, and other risks associated with any study participation (e.g. loss of confidentiality and fatigue and frustration from repeated evaluations):

**Confidentiality:** As with any study, there is a potential risk of loss of confidentiality. Consistent with the Federal guidelines, all patients and guardians will be informed of the federally mandated reporting laws for child abuse and neglect, verbally and in the written consent form. Therefore, if abuse or neglect is suspected the Department of Human Services will be called. Risks associated with this include embarrassment, legal consequences, and removal of the child from the parents'/legal guardians' home.

**Healthy Lifestyle Intervention (LIFE):** There is little to no risk associated with LIFE, although patients may become bored, fatigued or develop anxiety by the weight monitoring and recommendations. The exercises recommended may result in muscle soreness or strains, as there may be an increase in activity levels.

**MET:** All patients, guardians and clinicians will be made aware that MET is not approved by the USFDA for the treatment of overweight or obese youth or for SGA-related weight gain. Risks associated with MET include: Common side effects ( $\geq 5\%$ ): diarrhea, nausea, and vomiting. Less likely ( $< 5\%$ ): abdominal pain/abdominal distension, constipation, dizziness, dysguesia, dyspepsia, flatulence, headache, and upper respiratory infection. Rare: Lactic acidosis, 47 cases out of 1 million patients taking MET. Very rare: Vitamin B12 deficiency. Clinicians will be educated that youth who develop symptoms of lactic acidosis, such as hyperventilation, myalgia, malaise, and somnolence should stop taking MET and notify their treating clinician immediately. Additionally, we will educate all study-related clinicians about the very rare side effect of Vitamin B12 deficiency and associated potential clinical manifestations of vitamin B12 deficiency (i.e., peripheral neuropathy and pernicious anemia).

**Blood Draws:** Although blood draws are not required for participation in MOBILITY, they are highly encouraged in accordance with clinical practice guidelines. No study specific blood draws will be performed. Risks of blood draws include discomfort and/or bruising at the blood draw site. Less commonly, fainting, the formation of a small blood clot, swelling of the vein and surrounding tissue,

bleeding from the puncture site or infection may occur. Other potential risks include possible fatigue and frustration from repeated evaluations and the potential for additional weight gain, worsening of lipids, and increased insulin resistance. Since only patients prescribed SGAs as part of their clinical care will be approached for participation and no patient will be started on an SGA for the purpose of the study, we do not consider other risks associated with SGA treatment as study specific risks. Additionally, patients may experience exacerbation of BSD symptoms during study participation.

**Protection Against Risks.** The final protocol will be approved by the Steering and Family Advisory Committees, the CCHMC and NS/LIJ IRBs, and the study data and safety monitoring board (DSMB) prior to recruiting. Patients/parents will be clearly informed they are free to terminate participation at any point during study participation. Furthermore, to minimize risks associated with the study, all personnel will be thoroughly trained as previously described prior to having any contact with patients or data.

Breach of confidentiality: All data will be entered into electronic case report forms (eCRF) or directly into databases (e.g. patient/parent questionnaires) that are 21 CFR Part 11 and/or HIPAA compliant. We will train all study-related personnel to follow HIPAA regulations for research to ensure confidentiality of all data and that the rights of the patients/guardians are protected. All data will reside on password-protected computers, with only the investigators and key members of the research team having access. A variety of other measures will be taken to protect confidentiality, including: We will 1) assign and use a unique ID number to each patient to label all components of the protocol, instead of patient names, 2) restrict access to the key linking names and ID numbers to key staff and the PI at each site, 3) store of any paper with data at each site in a locked file cabinet, 4) if necessary, only send de-identified from clinical sites to the data coordinating site. Patients and caregivers will directly enter information regarding adherence, treatment satisfaction, mood, anxiety, QoL, and drug and nicotine use, into the tablet where it will go directly to the study database. Therefore, there is little information that site staff will collect and most of it is part of a standard clinical visit, so that the risk of loss of confidentiality is minimal.

Subjects will be told that agents of the Academic Health Center's IRB, study monitors, representatives from the USFDA or the study coordinating sites (UC/CCHMC or LIJ/NS), and members of the DSMB will be allowed to inspect sections of their medical and research records related to this study, if requested.

Site clinicians are federally mandated to report suspected abuse or neglect. However, we will encourage any such reports to be made with extreme confidentiality to the Department of Human Services. Healthy Lifestyle Intervention (LIFE): All patients and families will receive LIFE education from a clinical site staff member. [name] will ensure that all clinical site staff are adequately trained prior to initiating LIFE and will be available on an ongoing basis to all site staff that have questions about LIFE. The site staff will suggest that physical activity is spread over the course of 5 days (30 minutes/day) to achieve the recommended 150 hours/week, and not performed all at once to avoid muscle or other discomfort. The information that will be provided to the families outweighs the risks associated with LIFE.

MET: Metformin is USFDA approved to treat youth with diabetes type 2, > age 10. Additionally, there are significant safety data for MET down to age 8 years. However, since MET is not approved for the attenuation of weight gain in youth, we will submit a research IND to propose studying MET for this purpose and wait the required 30 days before initiating the study. We will follow all appropriate FDA guidelines for IND submissions. Additionally, [name] will be responsible for sending serious adverse events (SAEs) to the FDA, IRBs, and DSMB in a timely fashion in compliance of IND and FDA guidelines.

To further protect against the risks associated with metformin, patient, parent, and endocrinologist research team members will train clinical site staff prior to study initiation regarding the recommended MET dosing for the study, how to discuss MET with patients and families, common and less common side effects, and strategies to mitigate side effects (e.g. decrease dose and how to switch to MET-XR or take it with meals). This training will be taped and available online for any new clinician during the

course of the study. Our study endocrinologists (Drs. [name] and [name]) will also be available throughout the study should any site clinicians have questions regarding MET use. We will also educate site clinicians that it is part of standard of care to obtain labs prior to initiating MET. In particular, since MET is excreted by the kidneys, if a patient has creatinine  $\geq 1.3$  mg/dL on 2 occasions, they will be excluded from study participation and referred to their primary care clinician. Since lactic acidosis is a very rare side effect of MET and primarily occurs in elderly diabetic patients with significant renal insufficiency or congestive heart failure, we will inform clinicians of the risk and associated symptoms, but explain that we are excluding those most at risk and to our knowledge, that there have been no reports of lactic acidosis in youth. Additionally, we will encourage site clinicians to inform patients that excessive use of alcohol needs to be avoided as alcohol potentiates the effects of metformin on lactate metabolism (patients may be users of alcohol) and metformin should be discontinued prior to any IV radiocontrast study or surgical procedure. Additionally, to guard against risk, if a patient has two 8-hour fasting glucose levels  $\geq 126$  mg/dL, they will be referred to their primary care clinician (and if at screening they will not be included in the study), so that they may be evaluated for type II diabetes.

**Blood Draws:** We will recommend that only trained and certified phlebotomists draw blood at a certified laboratory facility.

**Other potential risks:** To guard against frustration and fatigue, questions and surveys have been carefully chosen by patients, parents, and stakeholders. However, when necessary, assessments can be divided to decrease the frustration and fatigue. In addition, research staff will be hired based on their research experience and work with children and adolescents. Lastly, patients and their parent(s)/legal guardian(s) will be advised that they do not have to participate in the study and that their participation is voluntary and refusal to participate will not impact their clinical care in any way. Their alternative to study participation is to continue to receive standard clinical care. **Additional weight gain or metabolic abnormalities:** Patients in the study will be closely monitored for weight gain and metabolic abnormalities. Clinicians, parents, or patients can discontinue assigned study treatment at any point, but will still be monitored for up to 24 month. If a patient continues to have substantial weight gain ( $> 10\%$ ) in the LIFE group, a clinician might decide to add MET to the treatment if clinically indicated. Likewise, if the patient is randomized to the MET + LIFE group and continues to have substantial weight ( $> 10\%$ ) they will have the option to continue MET and/or add another treatment or switch the patient's treatment for BSD, whichever is clinically indicated. If a participant's BMI percentile 5% (= underweight) his/her treatment with MET will be discontinued.

Although the risk of low vitamin B12 while taking MET is associated with age  $> 50$  years and having type II diabetes, we will encourage clinicians to monitor B12 levels and a CBC throughout study participation. We will educate all study-related clinicians about this potential side effect of metformin and the very rare clinical manifestations of MET-related vitamin B12 deficiency (i.e., peripheral neuropathy and pernicious anemia).

All changes will be noted, however since this is a pragmatic trial we will not mandate specific study discontinuation criteria, even if data collection is missed at recommended times for study visits. The intervals between study data collection are just guidelines for the most common intervals between clinical visits. However, clinical visits may occur more or less frequently. Regardless, data will be collected from participants at clinical visits, when feasible, at a frequency of no more than recommended in the Schedule of Events (Table 2). We will encourage clinicians to follow recommended guidelines for referrals and treat patients as clinically indicated. We will review guidelines at study initiation. For example, referrals to endocrine will be recommended for fasting glucose  $\geq 126$  mg/dL  $\times 2$ , HbA1C  $\geq 5.7\%$ , or fasting insulin  $\geq 50$  mcU/mL. Patients with LDL  $> 140$  or triglycerides  $> 300$  might be referred to a lipid clinic, or those with elevated liver enzymes ALT  $> 45$ , for a liver clinic for evaluation of non-alcoholic steatohepatitis (NASH). After a review of the literature and consulting with experts in the NASH field, we selected the

threshold for referral to liver clinic. Abnormal ALT will be defined as approximately 2x the upper limit of normal of the NHANES-derived population-based ULN ( $\geq 22.1$  for girls,  $\geq 25.8$  for males). Although the cutoff would be higher for boys, for consistency we will use a single cut-off of  $ALT >= 45$ . Referral for hypertension will be recommended if blood pressure is  $> 95\%$  at 3 times or  $> 130/90$ . Drs. [name] and [name] will facilitate referrals as clinically necessary to ensure patients safety.

We will monitor all patient records and train all clinicians to ensure that if they note a laboratory value as clinically significant, they will need to specify the recommended follow-up and outcome.

Exacerbation of BSD is also a risk, however patients will be treated for BSD as clinical indicated and there are no restrictions on psychotropic medications use. Patients will be monitored closely by site clinicians who will use the YMRS to systematically assess manic symptoms and the PHQ-9 item #9, to assess current suicidality. Patients will remain in the study even if they require a change in treatment or psychiatric hospitalization. These events will be recorded as psychiatric symptom burden outcomes. Patients who become pregnant during their study participation will continue to be followed. We will encourage treating clinicians to discontinue metformin if it is being prescribed for study participation and to consult with the prescribing clinician prior to discontinuation, if it is prescribed by another clinician and for reasons unrelated to the study.

**b. Anticipated Benefit Justifies the Risk** - We believe the risks associated with study participation are minimal. Despite patients being randomized to LIFE + MET or LIFE alone, this is a pragmatic observational study and there are minimal study specific procedures associated with participation. Additionally, patients will remain in the study and data will be collected regardless of whether they switch treatment arms or miss visits, although all of this information will be recorded. Youth with BSD taking SGAs receive low rates of basic metabolic monitoring and even lower rates of intervention for being overweight or obese, even though weight gain is the side effect of SGAs that causes them the most concern and is a common reason for poor adherence. Participation may increase their likelihood of receiving state-of-the art monitoring and intervention/prevention for weight gain, obesity, and metabolic disorders. Potential benefits also include the chance to contribute to a scientific investigation which may benefit other patients like themselves in the future. The study will benefit society as a whole by potentially providing clinicians with a new means to optimize efficacy, minimize risk for adverse reactions, and ultimately achieve better quality of life for patients treated with SGAs. We may also gain a better understanding of MET's effects on anthropomorphic measurements as well as glucose and lipid metabolism, which may ultimately improve our ability to prevent and/or manage the longer-term effects of SGA. Overall, the risks associated with this study are minimal and subjects may receive direct benefit from participation. Therefore, in the opinion of the research team, including patient, parent, and other stakeholders, the benefits of this study outweigh the risks.

In addition, the benefits of this pragmatic trial to society, as well as to individual patients, such as gaining important information about his/her mental and physical health status and receiving healthy lifestyle intervention and MET, far outweigh its minimal risks involved. This patient-centered study will enhance our understanding of the effectiveness in a community setting of LIFE and MET to abrogate weight gain and its patient-reported complications, such as poor adherence, treatment satisfaction, QoL and psychiatric symptoms burden in obese or overweight youth with BSD who are treated with SGAs. In summary, this study will provide critical information to address an important public health concern in a highly vulnerable population.

**c. Anticipated Benefit as Favorable as Alternative Approaches** – An alternative to study participation is not participating and receiving standard of care treatment as directed by a physician of that participant's choosing. Participation may increase their likelihood of receiving state-of-the art monitoring and intervention/prevention for weight gain, obesity, and metabolic disorders associated with SGAs.

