1. Patients will be excluded if they have had exposure to a total daily dose of MET 1000 mg bid for at least 2 weeks in the past 3 months;
2. Patients will be excluded if they could not tolerate MET during the recommended titration schedule outlined in the protocol;
3. Major neurological or medical illnesses that affect weight gain (e.g., unstable thyroid disease) or require a systemic medication that might impact weight or glucose regulation (e.g., diabetes mellitus [insulin], chronic renal failure [steroids]);
4. If lab results are available in the last 6 months, then a fasting serum glucose  $\geq 126 \text{ mg/dL}$  on two occasions prior to or during screening, indicating need for prompt treatment.
5. If lab results are available in the last 6 months, then a serum creatinine  $\geq 1.3 \text{ mg/dL}$  on two occasions during screening and/or follow-up, indicating potential impairment of renal functioning
6. Pregnant or breast feeding;
7. Based on their clinician's assessment, children and caregivers who are unable to complete screening/baseline assessments for any reason;

The enrollment rate will be approximately 1-2 patients/month/site for a recruitment time of 57 months.

**Randomization:** We will randomize 1800 patients (1:1 ratio) to either MET + LIFE or LIFE alone. All patients will receive a lifestyle intervention (LIFE) of brief standardized education. Once a patient is determined to meet the above criteria and has provided appropriate informed consent/assent, site staff will assign the participant a patient ID number. The site staff will then log on to the study's REDCap site and enter the Patient ID, and the following stratification factors: site, overweight or obese, previous SGA exposure, and sex of patient (transgendered patients will be randomized according to sex assigned at birth). REDCap has a built in mechanism that prevents duplication of subject ID numbers.

Once all stratification factors have been entered, the REDCap randomization module will return the next assignment for the appropriate strata.

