**Exclusion Criteria:**

1. Patients will be excluded if they have had exposure to a total daily dose of MET 1000 mg bid for at least 2 weeks in the past 3 months;
2. Patients will be excluded if they could not tolerate MET during the recommended titration schedule outlined in the protocol;
3. Major neurological or medical illnesses that affect weight gain (e.g., unstable thyroid disease) or require a systemic medication that might impact weight or glucose regulation (e.g., diabetes mellitus [insulin], chronic renal failure [steroids]);
4. If lab results are available in the last 6 months, then a fasting serum glucose  $\geq 126\text{ mg/dL}$  on 2 occasions prior to or during screening, indicating need for prompt treatment.
5. If lab results are available in the last 6 months, then a serum creatinine  $\geq 1.3\text{ mg/dL}$  on 2 occasions during screening and/or follow-up, indicating potential impairment of renal functioning
6. Pregnant or breast feeding;
7. Based on their clinician's assessment, children and caregivers who are unable to complete screening/baseline assessments for any reason;

If a patient does not have fasting glucose or renal lab results within 6 months prior to their baseline visit, then every attempt will be made to obtain labs prior to starting metformin. However, patients will not be excluded from the study if they are unable to get serum creatinine or glucose. Renal dysfunction is extremely rare in otherwise healthy children and adolescents, and in a clinical setting renal panels are not typically done prior to starting metformin, unless there is a reason to suspect kidney disease.

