The initial rationale for requiring normal glucose prior to starting metformin was that patients who are hyperglycemic may need to receive metformin + LIFE rather than LIFE alone. However, if a patient does not have a normal glucose available prior to randomization, but meets all other study criteria, we will continue to collect data from the patient and administer the treatment to which they have been randomized, so that at a minimum they will receive LIFE. We will also strongly encourage their clinician to emphasize the importance of obtaining fasting glucose levels. If, however, lab results are available in the last 6 months, patient with a fasting glucose  $\geq 126$  mg/dL on 2 occasions will be excluded and referred to their primary care clinician for prompt evaluation for Type II diabetes. Including these patients, rather than waiting until they get their glucose level checked, will ensure that at least the patient will receive LIFE while we encourage the clinician to engage the patient to get fasting metabolic labs. At any point in the study of a patient has a fasting glucose  $\geq 126$  mg/dL on 2 occasions, they will be immediately referred to their primary care physicians and possibly endocrinology.

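### The creatinine rule can be read to remove randomised patients during follow-up, against the trial's retention policy, and nothing says to stop metformin for that result

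*Combined protocol and SAP*

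**What the plan says.** **The creatinine rule.** Criterion 5 appears twice. In Section E.a it covers serum creatinine of 1.3 mg/dL or more "on two occasions during screening and/or follow-up, indicating potential impairment of renal functioning". In Section F (Exclusion Criteria) it reads "on 2 occasions during screening and/or follow-up, indicating potential impairment of renal functioning". Section G.a, under protection against metformin risks, says of a patient at or above 1.3 "mg/dL on 2 occasions, they will be excluded from study participation and referred to their primary care clinician".

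**The parallel glucose rule.** In the same paragraph of Section G.a, two fasting glucose values of 126 mg/dL or more lead to referral, with the limit "and if at screening they will not be included in the study". Section F says that if this happens at any point in the study, "they will be immediately referred to their primary care physicians and possibly endocrinology".

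**Retention.** Section G.a says that clinicians, parents or patients "can discontinue assigned study treatment at any point, but will still be monitored for up to 24 month". It also says: "Patients will remain in the study even if they require a change in treatment or psychiatric hospitalization". The same section states that, because the trial is pragmatic, it imposes no set criteria for discontinuing the study. Section G.b adds that data collection continues after a switch of arm or missed visits.

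**Stopping metformin.** A stop is stated for underweight (Sections E.a and G.a), symptoms of lactic acidosis (G.a) and before radiocontrast or surgery (G.a). For pregnancy, Section G.a has: "Patients who become pregnant during their study participation will continue to be followed. We will encourage treating clinicians to discontinue metformin". The text after Table 2 says that a renal panel before metformin is meant to detect impairment that would rule out its use.

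**The concern.** If criterion 5 operates after randomisation, two sites could treat the same patient in opposite ways and both cite the protocol. One would take the patient out of the study. The other would keep following, as the protocol provides after a treatment change, hospitalisation or pregnancy.

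Removal would be an avoidable post-randomisation exclusion. It would also apply to LIFE-only patients not taking metformin, for whom it offers no metformin-related protection. For a patient on metformin, leaving the study does not itself end the prescription, and ending it is what matters when renal clearance falls. What is at stake is the routine study data after removal and a clear instruction to the treating clinician.

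**Working it through.** The plan gives no figure to reproduce. The check is mainly a comparison of texts, followed by a rough size.

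**1. Does the rule reach past randomisation?** Criterion 5 names follow-up in both places. Criterion 4, on glucose, stops at screening. The Section G.a glucose rule carries a screening limit; the creatinine sentence in the same paragraph does not. Reading the creatinine rule as applying only at entry leaves the follow-up words in criterion 5 with no function. So the text permits removal after randomisation.

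**2. Could the situation arise?** Yes. Sections E.a and F allow enrolment, and continued participation, without baseline creatinine. Table 2 suggests renal panels at baseline, month 6 and month 24. A patient's first result may therefore come after randomisation.

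**3. Does it conflict with retention?** The clearest conflict is with the Section G.a statement that study discontinuation criteria are not mandated. The provisions on stopping treatment, treatment change, hospitalisation, pregnancy, arm switches and missed visits point the same way. None of them names creatinine, so the conflict is with the general policy.

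**4. Is there a metformin instruction?** The stops listed above do not include creatinine. The renal panel statement concerns not starting the drug. The example referral thresholds in Section G.a cover glucose, HbA1c, insulin, lipids, ALT and blood pressure, but not creatinine. Clinician discretion remains, together with a general duty to specify follow-up for laboratory values judged clinically significant.

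**5. How many patients?** The documents give no frequency; Section F calls renal dysfunction extremely rare in otherwise healthy youth. Assume 0.01% to 0.5%, with everyone tested:
- Total: 1800 × 0.0001 = 0.18 and 1800 × 0.005 = 9.
- Per arm: 900 × 0.0001 = 0.09 and 900 × 0.005 = 4.5.

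Fewer would be detected, because laboratory tests are optional.

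**6. Effect on the primary result.** The shift in an arm mean is the fraction removed times how far those patients differ from the rest. Taking the upper figure and an assumed difference of 1 SD in change: 4.5/900 × 1 SD = 0.005 SD.

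**7. Follow-up lost per removed patient.** If the two values fall at months 6 and 24, the loss is 24 − 24 = 0 months. If one value is at screening and the second near month 6, it is about 24 − 6 = 18 months. An off-schedule repeat before month 6 would lose more.

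**The case against.** The strongest reply is that removal is the less natural reading. Criterion 5 sits in an eligibility list and opens by looking back over the last six months of results. The Section G.a sentence follows directly on one about laboratory tests before metformin starts, and the next speaks of excluding those at greatest risk, which is selection language. No passage says that a randomised patient is withdrawn, and a site that relied on the no-mandated-discontinuation statement would keep following. This stands in part: taken alone, the Section G.a sentence can be a rule for before metformin starts. It does not explain why criterion 5 names follow-up in both places.

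A reader might infer that a patient with falling renal function is left on metformin without safeguards. The documents do not support that. Section G.a tells patients with symptoms of lactic acidosis to stop, requires a stop before radiocontrast or surgery, gives renal excretion as the reason for the creatinine rule, directs referral, and makes study endocrinologists available throughout. The monitoring board reviews adverse events and early withdrawals twice a year, and serious adverse events are followed to resolution or stabilisation. What is missing is one explicit sentence about creatinine during follow-up.

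It can also be said that advising a stop at 1.3 mg/dL is a new treatment rule in a trial that leaves care to clinicians. That is fair, and it is why the advice below is worded as encouragement.

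**Conclusion.** The point holds as a minor one. Criterion 5 and the Section G.a sentence, read together, permit a post-randomisation exclusion in either arm that the general retention policy would otherwise avoid, and no passage tells clinicians to stop metformin for confirmed high creatinine during follow-up.

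The conclusion rests on giving effect to the follow-up words in criterion 5. It does not show that the protocol requires withdrawal of randomised patients; the text permits it on a contestable reading. Nor does it support a claim of bias in the BMI z-score comparison: even the upper assumed frequency, with full testing and a 1 SD difference, moves an arm mean by 0.005 SD. The issue is uniform handling across sites and a clear safety instruction for a very small number of patients.

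**What to change.** 1. In criterion 5, in both Section E.a and Section F, delete the reference to follow-up.
2. In Section G.a, limit the creatinine exclusion to screening, as is already done for glucose.
3. Add a rule for after randomisation: if creatinine is 1.3 mg/dL or more on two occasions, clinicians are encouraged to discontinue metformin, if it is prescribed, and to refer to primary care, while the patient continues to be followed to month 24. This keeps the protocol's threshold and takes the form of its pregnancy rule.
4. Report by arm any randomised patient already removed under the current wording.

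The cost is wording in three places and one notice to sites, with no added visits or tests. Clinician discretion is slightly narrower for very few patients.
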